8.1 Specification, Timing and Recording of Safety Parameters

A trained medical doctor will be available/present at all times and on all study days and be responsible for confirmation of suitability to participate, dosing, reviewing AEs, management of any side effects or medical events and discharge. At each study visit the study physician or delegate will carry out a physical exam, vital signs (blood pressure, heart rate, body temperature and respiratory rate) and ECG which will be recorded at each visit.

Participants will also be called daily to confirm they have taken the medication and for adverse event monitoring.

8.2 Procedures for Recording and Reporting Adverse Events

The Medicines for Human Use (Clinical Trials) Regulations 2004 and Amended Regulations 2006 gives the following definitions:

Adverse Event (AE): Any untoward medical occurrence in a subject to whom a medicinal product has been administered including occurrences which are not necessarily caused by or related to that product.

Adverse Reaction (AR): Any untoward and unintended response in a subject to an investigational medicinal product which is related to any dose administered to that subject.

Unexpected Adverse Reaction (UAR): An adverse reaction the nature and severity of which is not consistent with the information about the medicinal product in question set out in:

The Investigator's Brochure (IB) relating to the trial in question (for any other investigational product)

Serious adverse Event (SAE), Serious Adverse Reaction (SAR) or Unexpected Serious Adverse Reaction (USAR): Any adverse event, adverse reaction or unexpected adverse reaction, respectively, that

- Results in death;
- Is life-threatening;
- Required hospitalisation or prolongation of existing hospitalisation;
- Results in persistent or significant disability or incapacity;
- Consists of a congenital anomaly or birth defect.

Important Medical Events (IME) & Pregnancy

Events that may not be immediately life-threatening or result in death or hospitalisation but may jeopardise the patient or may require intervention to prevent one of the other outcomes listed in the definition above should also be considered serious.

Although not a serious adverse event, any unplanned pregnancy will also be reported via the SAE reporting system and to AstraZeneca. As outlined in the exclusion criteria, females of child bearing potential will not be included in the study.

Reporting Responsibilities

King's College London and King's College Hospital have delegated the delivery of the Sponsor's responsibility for Pharmacovigilance (as defined in Regulation 5 of the Medicines for Human Use (Clinical Trials) Regulations 2004 to the King's Health Partners Clinical Trials Office (KHP-CTO).

All SAEs, SARs and SUSARs (excepting those specified in this protocol as not requiring reporting) will be reported immediately by the Chief Investigator (and certainly no later than 24hrs) to the KHP-CTO in accordance with the current Pharmacovigilance Policy. In addition, all SAEs, SARs and SUSARs will be reported to AstraZeneca via Kinapse ([contact]) according to the timelines outlined in Appendix A and to the research ethics committee (REC).

Death as a result of disease progression and other events that are primary or secondary outcome measures are not considered to be SAEs and should be reported in the normal way, on the appropriate CRF.

The KHP-CTO will report SUSARs to the regulatory authorities (REC, competent authorities of other EEA (European Economic Area) states in which the trial is taking place.

The Chief Investigator will report to the relevant ethics committee. Reporting timelines are as follows:

- SUSARs which are fatal or life-threatening must be reported not later than 7 days to

the sponsor and reported to Kinapse as they occur and within 24 hours of knowledge. SAEs will be reported to Kinapse on a quarterly basis. Any additional relevant information must be reported within a further 8 days.

- SUSARs that are not fatal or life-threatening must be reported to Kinapse within 24 hours of the sponsor first becoming aware of the reaction.
- The Chief Investigator and KHP-CTO (on behalf of the co-sponsors), will submit a Development Safety Update Report (DSUR) relating to this trial study drug, to the REC annually.

8.2.1 Adverse events that do not require reporting

All reporting of adverse events will be as per usual standards. All adverse events will be reported, except for ongoing symptoms due to their illness. Any changes will be recorded as adverse events.

8.3 Treatment Stopping Rules

Subjects may be discontinued from the study drug in the following situations. Note that discontinuation from study treatment is NOT the same thing as a complete withdrawal from the study (i.e. data collected may still be used in data analysis).

- Subject decision. The subject is at any time free to discontinue treatment, without prejudice to further treatment. In this case, the subject will have a follow up phone call and at the discretion of a study physician, will be invited for an early termination visit.
- Adverse Event
- Severe non-compliance with the Clinical Study Protocol
- Safety reasons as judged by the investigator and/or sponsor and/or safety advisory committee where continued treatment may put patient at undue risk.

8.3.1 Study termination

A study advisory committee will be set-up including representatives from the study team, the clinical team, AZ and an independent chair. This committee will meet every six months to review all AE, SAE and SUSAR data as well as study progress. The committee can advise pausing or stopping the study. Any member of this committee will be able to call an ad-hoc meeting if deemed necessary based on the AE reporting for this or other studies using Saracatinib.

If the trial is prematurely discontinued, active participants will be informed and no further participant data will be collected. The Competent Authority and Research Ethics

Committee will be informed within 15 days of the early termination of the trial.

9 Statistics

9.1 Sample Size

A group of approximately 30 with PD Psychosis will be enrolled in the study for 26 completers.

We used the results from (Meppelink et al., 2009), to estimate statistical power to detect the attenuation in the brain activity impairments prior to and during ‘pop-out’ recognition of degraded stimuli. This activity is reduced in those with PD psychosis with visual hallucinations compared to those without hallucinations. The signal reduction is greatest immediately before target detection or ‘pop-out’ in clusters with peaks in the occipital lobe and fusiform gyrus extending into the posterior lateral temporal lobes. The signal changes from the bilateral peaks in the fusiform gyrus were used for the power calculation. An effect size of 2/3 of that seen in Meppelink was used as a conservative estimate of the predicted change with Saracatinib (see below for justification of effect). For left fusiform prior to ‘pop-out’ the power calculation was for an effect size of 0.91 ($0.66 * 1.39$) and SD of 0.048 on the mean difference of 0.0462 requiring 15 patients with a power of 0.9 and alpha of 0.05, or 20 patients with alpha=0.01. The same calculation for the right fusiform gyrus gives a sample size of 13 patients for an effect size of 1.26 and alpha=0.01 (or a difference of 0.0595 with an SD of the difference of 0.046). Based on these calculations we propose to recruit 30 patients for at least 26 completers, with a primary endpoint of change in activity in the fusiform/posterior lateral temporal lobes. Drop-outs may be replaced at the discretion of the investigator.

For fMRI power calculations: A change in fMRI signal would indicate support for the modulation of the hypothesized mechanism. This is generally considered a valuable goal in proof of mechanism experimental studies. Understanding if the effect size of the fMRI signal change is clinically meaningful (i.e. likely to result in symptom improvement) would provide a stronger platform for translating findings for patient benefit and potentially aid outcome measure and dose selection. There are many examples of treatment studies in which fMRI changes are accompanied by symptomatic improvement. For example, in patients with psychosis (unrelated to Parkinson’s disease) and other

psychiatric disorders such as depression studies show that activation, connectivity and multivariate patterns can normalize with treatment effects [(Abbott et al., 2013), (Rubia et al., 2011)]. When studies have reported brain activation levels, existing treatments do not reverse, but instead reduce impairments. For example, responders to antidepressants show a 2/3 reduction in amygdala activation abnormality compared to no change in non-responders (Williams et al., 2015) and frontal cortex impairments reduce by a similar amount after successful antipsychotic treatment in patients with schizophrenia (Snitz et al., 2005), leading to the hypothesis that a reduction of 2/3 impairment in brain activation is a valid target for predicting symptom improvement.

9.2 Randomisation

Subjects will be randomised into the trial on a 1:1 basis provided they have satisfied all subject selection criteria. Each subject will be assigned to a treatment arm by the means of a computer-generated pseudo code.

9.3 Analysis

A statistical analysis plan (SAP) will be prepared and finalised prior to un-blinding of treatment assignments. This document will provide further details regarding the definition of analysis variables and analysis methodology to address all study objectives.

We will be running a mixed effect analysis for the primary endpoints. Dropouts or missing data will not be included in the final analysis. For each analysis statistical outliers (2 SDs from mean) will be removed. Analyses with and without outliers will be provided for transparency as will a mixed effects analysis with all the data.

EEG data will be cleaned of artefacts and filtered before comparing N1 components of standard and deviant stimuli in an oddball paradigm. MRI data will go through standard pre-processing (i.e. movement correction and spatial normalisation) in SPM before fitting models of visual task events for each session (see below). These steps will occur at the single subject level and therefore will not require unblinding after this, single subject (or first level) analysis will be combined for group analysis. For the primary endpoints, the regions of interest data will be extracted and analysed using mixed effects models.

ROI Analyses

ROI endpoints will be calculated as the mean fit (beta) of the BOLD response to the task parameters within each hemisphere of the predefined brain region- inferior posterior aspect of the ventral visual system defined as a cluster peak in the fusiform gyrus extend into the lateral temporal cortex and occipital lobe. This data will be derived from

individual sessions and will be blinded to the treatment. Following unblinding, the primary comparison of interest will evaluate the effect of saracatinib in attenuating the reduced response on the visual recognition tasks, compared to placebo. The conditions to be compared are thus:

- Saracatinib vs placebo: during visual processing task
- Saracatinib vs placebo: during visual pop-out recognition

In addition, placebo scans will be compared to patients with psychosis to confirm regional brain differences.

These comparisons will be made using mixed effects models (with unstructured covariance) with fixed factors of drug (saracatinib or placebo) and session number (first or second), and a random effect of subject.

Pre-processing for ROI analysis will be identical to pre-processing for the image based analysis described below.

Image-based analyses

Image analysis will be analogous to the ROI approach, but to map at a higher spatial resolution, univariate effects. Pre-processing steps for the images will be conducted in a fixed, full-release version of SPM.

1. Slice timing correction: For each volume of the time series, a correction is performed for the differences in acquisition time between the slices with the middle slice used as reference.
2. Motion correction: For each time series, two-pass motion correction will be used. Total frame wise displacement (FD) will be calculated per volume and used to compare movement across sessions, and define movement spikes (>1mm) which will be used to derive a control regressor. If >10% of volumes are classified as spikes the particular fMRI time series will be excluded.
3. Co-registration: All the fMRI time series are co-registered using affine transformation to the same individual's T1-weighted scan.
4. Spatial normalization: All images will be registered to the standard-space (Montreal Neurological Institute) reference image. Non-linear warping will be used as per current best-practice.
5. Spatial smoothing: Data will be spatially smoothed with a Gaussian kernel (FWHM 6-8mm) to allow for gyral variability across subjects, improve the signal-to-noise ratio and ensure that the data be consistent with the assumptions of Gaussian Random Field theory used for the multiple comparisons corrections in the parametric image analysis.

Task based modelling

Onset times for events during each condition will be used to model the haemodynamic response using first level models of each session individually. For the Kanizsa task, the events are the presentation of each moving stimulus for each of the different conditions. For the visual pop-out task a finite impulse response function model will be used and will be time-locked to the detection point for the stimuli (the 'pop-out'). The time just prior to the recognition will be used for the primary end-point analysis.

EEG Data

The MMN will be analysed using the 'Neuroscan' software. Pre-processing: The slow ocular artefacts will be removed by regression with eye channels, and the data will be re-referenced to the average of the left and right Mastoids. After applying suitable filters (low pass and high pass), and rejecting any segments with gross artefact contamination, ERPs will be formed separately to the deviant/target and standard tones. The feature to be extracted for the MMN task is the magnitude in the most negative peak in the baseline corrected difference wave between the deviant and standard ERP. It is around 100 to 200ms after the deviance in the stimuli. It will be determined at FZ.

Behavioural data

Behavioural data will be summarized as means and standard deviations per subject per session and tested for normality using Shapiro-Wilk test and resulting deviations will be corrected using logarithm or square root transformations as appropriate. If reaction time data deviates from normality after transformation medians will be used for all analyses. Differences between groups will be tested with ANOVA models and drug effects with mixed effects models with fixed factors of drug (saracatinib or placebo) and session number (first or second), and a random effect of subject. We will consider use of unstructured covariance if there are sufficient degrees of freedom.

Pharmacokinetic Analyses

The plasma concentration of saracatinib will be assayed using samples taken just prior to and following the fMRI and EEG assessments and regressed against the fMRI and EEG endpoints in an exploratory analysis.

Safety Analyses

Safety parameters that will be assessed include pathology laboratory parameters, vital signs and adverse events. The parameters will be listed and summarized using standard descriptive statistics (where appropriate).

Audit trail

All recordings and processing steps will be logged and any scripts for the analyses will be saved.

10 Direct Access to Source Data and Documents

The Investigator(s) will permit trial-related monitoring, audits, REC review, and regulatory inspections by providing the Sponsor(s), Regulators and REC direct access to source data and other documents (e.g. patients' case sheets, blood test reports, X-ray reports, histology reports etc.).

11 Ethics & Regulatory Approvals

The trial will be conducted in compliance with the principles of the Declaration of Helsinki (1996), the principles of GCP and in accordance with all applicable regulatory requirements including but not limited to the Research Governance Framework and the Medicines for Human Use (Clinical Trial) Regulations 2004, as amended in 2006 and any subsequent amendments.

This protocol and related documents will be submitted for review to the Research Ethics Committee (REC), and to the Medicines and Healthcare products Regulatory Agency (MHRA) for Clinical Trial Authorisation

The Chief Investigator will submit a final report at conclusion of the trial to the KHP-CTO (on behalf of the Sponsor), the REC and the MHRA within the timelines defined in the Regulations.

The investigator must ensure that each study subject, or his/her legally acceptable representative, is fully informed about the nature and objectives of the study and possible risks associated with participation. The investigator, or a person designated by the investigator, will obtain written informed consent from each subject or the subject's legally acceptable representative before any study specific activity is performed. The informed consent form used in this study, and any changes made during the course of the study must be prospectively approved by the REC and HRA before use. The investigator will retain the original of each subjects' signed consent form.

12 Quality Assurance

Monitoring of this trial will be to ensure compliance with Good Clinical Practice and scientific integrity will be managed and oversight retained, by the KHP-CTO Quality Team.

Data handling, record keeping, quality control and quality assurance will adhere to the procedures to be outlined in the documentation of the Neuropharmacology Section of the Department of Neuroimaging, IoPPN, KCL. These are available on request from [contact].

13 Data Handling

The Chief Investigator will act as custodian for the trial data. The following guidelines will be strictly adhered to:

Patient data will be anonymised.

- All anonymised data will be stored on a password protected computer.
- All trial data will be stored in line with the Medicines for Human Use (Clinical Trials) Amended Regulations 2006 and the Data Protection Act and archived in line with the Medicines for Human Use (Clinical Trials) Amended Regulations 2006 as defined in the Kings Health Partners Clinical Trials Office Archiving SOP.

14 Data Management

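### Section 9.3 removes endpoint values beyond 2 SD without defining the rule or naming the deciding run; under most readings this biases the drug-placebo estimate or makes its interval too short

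*Combined protocol and SAP*

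**What the plan says.** Section 9.3 (Analysis) sets the rule: "For each analysis statistical outliers (2 SDs from mean) will be removed". It continues: "Analyses with and without outliers will be provided for transparency as will a mixed effects analysis with all the data". On incomplete data it says: "Dropouts or missing data will not be included in the final analysis".

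Three other statements bear on the rule:
- Under ROI Analyses, the endpoint values are to come from "individual sessions and will be blinded to the treatment". This covers how the values are derived. It does not mention the outlier step.
- Further analysis detail is deferred: "A statistical analysis plan (SAP) will be prepared and finalised prior to un-blinding of treatment assignments".
- Under Image-based analyses there is a separate exclusion that does not look at the endpoint value: "If >10% of volumes are classified as spikes the particular fMRI time series will be excluded".

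Section 9.3 does not state the reference mean and SD (drug-placebo differences, each drug, each session, or all values pooled), the timing of removal relative to unblinding, or whether a removed value takes its partner session with it. It also does not say outright which run answers the primary objective.

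**The concern.** The rule discards data according to the size of the endpoint itself. With normal data and no artefact at all, it still removes about 0.7 to 2.2 of 26 patients whose values are ordinary.

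The effect depends on which values are cut:
- **Removal using drug labels** (drug-minus-placebo differences, or each drug separately) leaves the estimate centred but makes its standard error too small.
- **Removal ignoring drug labels**, applied to session values or session differences, keeps the null p-value valid. However, it preferentially removes values that carry the drug effect, so the estimate moves towards zero and the interval is too short.

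Section 9.1 uses the size of the signal change, two-thirds of the impairment, as the target for predicting symptom improvement, so bias in the estimate matters even when the test result does not change. If the trimmed and untrimmed results disagree, no explicit rule settles which one counts.

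**Working it through.** **Inputs.** There are 26 completers (section 9.1), 13 per sequence (balanced, section 5.5.1). Left fusiform: "SD of 0.048 on the mean difference of 0.0462", so 0.0462/0.048 = 0.96. Right fusiform: "a difference of 0.0595 with an SD of the difference of 0.046", so 0.0595/0.046 = 1.29. The stated left effect size is 0.91. Within-patient correlation (rho) is not given; 0 to 0.9 is assumed. Tests are two-sided at 5%.

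**The plan's own figures.** With a paired t-test at 90% power, effect 0.91 and alpha 0.05 give 15 patients, as stated. At alpha 0.01, 0.0462/0.048 gives 20 as stated (0.91 gives 22), and the right fusiform gives 13 as stated. With no removal, n = 26 and effect 0.91, power is 99.4%.

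**Hand check 1: drug-minus-placebo cut.** A 2-SD cut keeps a share 0.9545 of a normal sample. The variance of the kept values is 1 - 4(0.05399)/0.9545 = 0.774 of the true variance. The reported squared SE is therefore proportional to 0.774/0.9545 = 0.811. The cut limits move with the sample mean, so the true squared SE is proportional to [0.7385(1 + 2 x 0.2160) + 0.2160^2]/0.9545^2 = 1.212. Here 0.2160 = 4 x 0.05399 and 0.7385 = 0.9545 - 0.2160. The SE ratio is sqrt(0.811/1.212) = 0.82, and large-sample rejection under the null is 2[1 - Phi(1.96 x 0.818)] = 10.9%. Simulation at n = 26 gives 10.1-10.2%.

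**Hand check 2: session-difference cut (session 2 minus session 1).** The two sequences centre at +0.0462 and -0.0462. The overall SD is sqrt(0.048^2 + 0.0462^2) = 0.0666, so the limits are +/-0.133. For patients given drug second, these lie (0.1332 - 0.0462)/0.048 = 1.81 SD above their mean but (0.1332 + 0.0462)/0.048 = 3.74 SD below it. The cut therefore falls almost wholly on large drug effects, and the other sequence mirrors this.

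**Simulation.** SD of the difference is fixed at 0.048. *Pairs dropped*: the patient is removed; period-adjusted t-test; 60,000 trials per setting. *Partner kept*: REML random-subject model with drug and session effects; 20,000 trials per setting. Ranges run over rho 0 to 0.9.

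| Cut ignoring drug labels | Planned 0.0462 estimated as | Too small by | 95% interval covers |
|---|---|---|---|
| Session difference | 0.0431-0.0432 | 6.5-6.7% | 89% |
| Per session, pairs dropped | 0.0411-0.0450 | 11.0-2.5% | 88-95% |
| Per session, partner kept | 0.0408-0.0442 | 11.6-4.3% | 87-94% |
| Pooled, pairs dropped | 0.0407-0.0447 | 11.9-3.2% | 87-95% |
| Pooled, partner kept | 0.0400-0.0436 | 13.3-5.7% | 85-94% |

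Type I error in these rows is 4.8-5.7%. For the right fusiform with pairs dropped, the estimate is 2.2-8.1% too small.

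| Cut using drug labels | Type I error at rho 0 / 0.3 / 0.5 / 0.7 / 0.9 |
|---|---|
| Drug-minus-placebo difference | 10.1-10.2% throughout (coverage 90%) |
| Per drug, pairs dropped | 9.6 / 8.5 / 7.2 / 6.5 / 5.5% |
| Per drug, partner kept | 10.7 / 9.3 / 8.5 / 7.5 / 5.7% |
| No removal, t-test | 4.9-5.1% throughout (coverage 95%) |
| No removal, REML | 5.9 / 5.2 / 4.9 / 4.8 / 4.9% |

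The 10.7% peak should be read against the last row: about 0.8-0.9 points of it are present in the REML test without any trimming.

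**Limits and sensitivity.**
- A cut on each patient's two-session average changes the estimate by no more than 0.4% and leaves coverage at 95%.
- At effect 0.91 the label-free shrinkage is 2.5-13.6% and power is at least 96%.
- With heavier-tailed errors (t with 4 df), label-using type I error is 5.3-9.6% and label-free shrinkage is 2.3-11.4%.
- Repeating the drug-minus-placebo cut until nothing more is removed raises type I error to about 17%.
- At an assumed smaller effect of 0.5 SD with pairs dropped, label-free cuts on session values or differences lower power from 69% to 56-65%.

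**The case against.** **The plan already has safeguards.** It promises results with and without outliers, a mixed model on all data, and a SAP finalised before unblinding. This stands in part: the untrimmed result will be visible, and nothing suggests it would be withheld. But none of these statements reverses the removal or says which run decides.

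**An order among the runs is implied.** Mandatory removal, followed by other runs offered for openness, reads naturally as trimmed first. That is fair, so it would be too strong to say the plan has no hierarchy. The hierarchy is implicit, and the run it favours is the one with the poorer properties on clean data.

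**Type I error may not be affected.** A reader might infer that the primary test runs at double its nominal error. The documents do not support that: it requires a cut that uses drug labels, and the ROI values are derived blind. The reading closest to that text keeps type I error near 5%. A reader might also infer that any blind cut biases the estimate; the two-session average shows otherwise.

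**The largest figures rest on low rho.** A crossover was chosen because patients serve as their own comparators (section 2.3), so rho near 0 is the least natural case, and single-value cuts are nearly harmless at 0.9. The session-difference shrinkage (about 7%) and the drug-difference type I error (about 10%) do not depend on rho.

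**The model differs.** Section 9.3 names an unstructured covariance; the simulations use a t-test or a random-intercept model with equal variances. This remains an approximation.

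**Trimming protects against artefact.** It does when contamination is heavy; the cost is given with the fix.

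**Conclusion.** The point holds as an underspecified rule that, under most but not all readings, gives a worse result than no removal. On the reading closest to the blinded ROI data, the planned left-fusiform difference is understated by about 2.5-13% (about 7% for a session-difference cut) and 95% intervals cover about 85-95%. If drug labels are used, type I error is about 5.5-10%.

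It would be wrong to conclude that the trial is likely to miss its planned effect: power there stays at about 96% or more. The power loss at 0.5 SD rests on an effect size that the documents do not give. The sizes assume a one-pass cut, clean normal data, n = 26 and rho between 0 and 0.9. The omission is certain; the size of the harm depends on the reading and on rho.

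**What to change.** Amend section 9.3 and carry the same text into the SAP before unblinding:
1. Name the mixed model on all usable sessions, which is already planned, as the primary analysis.
2. Base exclusions from it on quality criteria whose thresholds are fixed before unblinding, such as the spike-volume rule, and not on the size of the endpoint value.
3. Keep the 2-SD run as a sensitivity analysis. State its reference mean and SD, that the cut is made once, what happens to the partner session, and that it is applied blind to drug.

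This takes two or three sentences and no new data or runs.

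The downside is that genuine extremes stay in the primary model. Suppose heavy artefact escapes the quality checks, assumed here as 5% of differences having five times the SD. The all-data interval is then 1.12/0.80 = 1.40 times as wide as with clean data, and power is about 88%, against 98-99% for trimmed runs. Under milder assumptions (2% at five times, or 5% at three times the SD), all-data power is 95-96%. In all three cases all-data coverage is 95-96%, against 90-92% when trimmed. The sensitivity run would reveal the problem.

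If the team prefers the trimmed run as primary, the minimum is to say so explicitly and to define the same items as in step 3. That closes the gap in the text but not the bias or the under-coverage, unless the chosen rule is one of the harmless ones.

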The scanning protocol will comprise a localiser to ensure a good positioning in the scanner, T1-weighted structural scan (to allow registration to a template), multi-echo resting state scan (for connectivity), Kanizsa illusion, the Meppelink task and a perfusion scan using pseudo-continuous ASL (to determine changes in neurovascular coupling caused by the drug).

Kanizsa Illusion

The Kanizsa task is a task that comprises of illusory contours which are perceived edges that 'bridge gaps between aligned luminance edges' but do not exist physically. The Kanizsa task is a task that used the perceived edges to give a direct comparison of the physiological response to illusory contours which may reveal information about object perception (Mendola et al., 1999). This task will take approximately 12 minutes.

Visual pop-out task (Meppelink task)

A visual task where objects, animals and people appear out of noise and participants must press a button when they recognise what it is. A previous study by Meppelink et. Al. reported that patients with visual hallucinations and Parkinson's disease had decreased activation of the lateral occipital cortex several seconds before image recognition compared to patients with PD but no psychosis and healthy controls (Meppelink et al., 2009). This task consists of 50 images appearing from noise and each video lasts for 30 seconds. In total, the task will take approximately 20 minutes.

Visual analogue scales of physical fatigue, mental fatigue and overall health

Visual scales ranging from 0-100 where the patient marks on the scale how they would rate their physical fatigue, mental fatigue, and overall health today.

PDQ

The Parkinson’s disease questionnaire is a quality of life questionnaire specific to Parkinson’s disease (Young et al., 2013). It is composed of 39 questions and participants are asked to read a statement and indicate on a scale of ‘Never’ to ‘Always or cannot do at all’ which applies best. The questionnaire assesses difficulties of daily living across 8 dimensions. The scale can provide a single figure that can be used to assess the overall quality of life related to health.

EQ-5D

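### Unrecognised pop-out images have no reaction time, so a per-session mean or median shrinks any drug effect on recognition time by an amount that depends on the unstated share recognised

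*Combined protocol and SAP*

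**What the plan says.** Section 6.2.2 describes the visual pop-out (Meppelink) task: "This task consists of 50 images appearing from noise and each video lasts for 30 seconds". Pictures emerge from noise and "participants must press a button when they recognise what it is".

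Section 9.3, under the behavioural data heading, sets one rule for all behavioural measures: "Behavioural data will be summarized as means and standard deviations per subject per session and tested for normality using Shapiro-Wilk test". Departures from normality are handled by a log or square-root transformation, and then: "If reaction time data deviates from normality after transformation medians will be used for all analyses". Drug effects are tested in a mixed model with drug and session as fixed factors and subject as a random effect.

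Two general rules in section 9.3 also bear on this: "Dropouts or missing data will not be included in the final analysis" and "For each analysis statistical outliers (2 SDs from mean) will be removed". Analyses with and without outliers, and a mixed-effects analysis of all the data, are promised as well.

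The documents do not say how an image that was never recognised enters the reaction-time summary, how many such images are expected, or whether the share recognised will be compared between treatments.

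**The concern.** When a video ends without a button press, the recognition time is not unknown in the ordinary sense. It is known to exceed 30 s, so it is right-censored. A mean or median taken over button presses alone conditions on recognition, and treatment may itself change recognition.

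If the drug speeds recognition, some images missed on placebo are recognised on drug, typically late in the video. They enter the drug session's average as long times, while the same images contribute nothing to the placebo average. The two sessions then average over different sets of images and the difference is pulled toward zero. A normality test, a transformation or a switch to medians does not change which images are included.

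What is at stake is the behavioural drug-effect estimate and its use beside the imaging. The first-level model for the primary endpoint is time-locked to the detection point (section 9.3, task based modelling), so unrecognised images cannot contribute there either. The share recognised under each treatment is therefore useful context for reading the BOLD result, and no comparison of it is planned.

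**Working it through.** The plan gives no figure for recognition time or for the share recognised, so there is nothing of its own to reproduce. Its power calculation concerns the fMRI signal only.

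**Inputs.** From section 6.2.2: 50 images per session and a limit L = 30 s. Everything else is an assumption: log-normal recognition times with placebo median m and log-SD s, and a drug that shortens every time by 15% (median 0.85m). The stated task length does not reveal the share recognised. 50 × 30 s = 25 min, yet "In total, the task will take approximately 20 minutes", and the text does not say whether a video stops at the button press.

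**Formulas**, with z = ln(L/m)/s and Φ the standard normal distribution function:
- share recognised: p = Φ(z)
- latent mean over all images: E = m·exp(s²/2)
- mean over recognised images only: R = E·Φ(z − s)/p
- mean with unrecognised images set to 30 s: C = p·R + 30(1 − p)
- median over recognised images only: m·exp(s·Φ⁻¹(p/2))

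**Worked case, m = 20 s, s = 0.5** (results from unrounded values):

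| | Placebo (m = 20) | Drug (m = 17) | Difference (s) |
|---|---|---|---|
| z | 0.811 | 1.136 | |
| p | 0.791 | 0.872 | |
| E | 22.663 | 19.264 | 3.399 |
| Φ(z − s) | 0.622 | 0.738 | |
| R | 17.816 | 16.294 | 1.522 |
| C | 20.359 | 18.048 | 2.311 |
| Recognised-only median | 17.52 | 15.68 | 1.84 |

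- Against the latent mean: 1.522/3.399 = 45% kept, 55% hidden.
- Against the capped mean, which the task can observe: 1.522/2.311 = 66% kept, 34% hidden.
- The fallback median shows 1.84 s against a true 20 − 17 = 3.00 s: 61% kept, 39% hidden.

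**When recognition is nearly complete**, again with 15% shortening:

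| m, s | Recognised on placebo | E difference (s) | R difference (s) | Hidden |
|---|---|---|---|---|
| 15 s, 0.30 | 99% | 2.354 | 2.210 | 6% |
| 18 s, 0.25 | 98% | 2.786 | 2.542 | 9% |
| 15 s, 0.40 | 96% | 2.437 | 1.942 | 20% |

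**Wider ranges.** Log-normal medians of 15 to 22 s, log-SD 0.5 to 0.7 and shortening of 10% to 20% correspond to 67-92% recognised on placebo. The recognised-only mean then keeps 25-67% of the latent effect, or 58-77% of the capped effect. Across normal times (SD 4 to 8 s, 2 s faster on drug) and log-normal (log-SD 0.2 to 0.5), exponential and Weibull times (each 10% shorter on drug), the hidden share of the latent effect is 4-19% at 99% recognised and 34-79% at 80%. Against the capped mean these become 3-15% and 24-59%. The direction was toward zero in every scenario, and the sign was always preserved.

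**The case against.** Several objections have force.

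- **The plan never says that only recognised images are averaged.** That is an inference from the button-press response and the missing-data rule. Unrecognised images could be set to 30 s and averaged. The behavioural paragraph is also generic, and section 9.3 says of the later SAP: "This document will provide further details regarding the definition of analysis variables and analysis methodology to address all study objectives". This stands as a limit on certainty. But the protocol already fixes the summary statistic, and an analysis of all the data cannot include a value that does not exist, so recognised-only averaging remains the natural reading unless the SAP says otherwise.
- **The size is not documented.** A reader might infer that about half of a true improvement would be lost. The documents do not support that: it needs a recognition share near 79% with the assumed log-normal spread, and a benchmark that counts times after the video has ended. If nearly all images are recognised, the bias is small.
- **The measure is not an endpoint.** Recognition time appears in none of the primary, secondary or exploratory lists in section 3.1, and section 7 says the study is powered for the fMRI signal. This stands.
- **A shrunken estimate is not a lost test.** A reader might infer that a positive imaging result would be left without behavioural support. That is not shown. An illustrative simulation of 26 patients found no consistent power loss for the recognised-only mean, and a per-session median with unrecognised images capped at 30 s had lower power than that mean.

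**Conclusion.** The point holds as a bias in estimation of uncertain size. On the natural reading of sections 6.2.2 and 9.3, pop-out reaction time is summarised over recognised images only, and the drug effect on recognition time is shrunk toward zero whenever the drug raises the share recognised. With 15% shortening and log-normal times, the loss runs from about 6-9% of the latent mean effect at 98-99% recognised on placebo to about 55% at 79% (about 34% against the capped mean). These figures rest on an assumed distribution, drug effect and recognition share; only the 30 s limit is documented. The consequence is confined to the behavioural drug-effect result and its use in interpreting the imaging. It is worth correcting before unblinding because the remedy is cheap and removes the conditioning on recognition.

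**What to change.** In the SAP, before unblinding, replace the per-session mean and the Shapiro-Wilk step for pop-out reaction time. Analyse image-level time to recognition as right-censored at 30 s, for example with an accelerated-failure or Cox model, with drug and session as fixed effects and a patient random effect. Report the proportion of images recognised by treatment. State explicitly that an image with no button press is censored, not missing, so that the general missing-data rule does not remove it.

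The cost is SAP wording and a little more analysis work on data already recorded. Visits, task and sample size do not change.
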